Title: Effects of using the Duracore Splinting Device on Patient Outcomes Related to Chest Trauma

Protocol Version Number: 3

Protocol Version Date: 12/8/2020

CHIRB IRBNet ID: 1517921-3

1) Investigators

Principal Investigator

[name] Title: Registered Respiratory Therapist Department: Respiratory Therapy [contact] Email: [contact]

Co-Investigator:

[name] Title: Registered Respiratory Therapist Department: Respiratory Therapy [contact] Email: [contact]

Co-Investigator:

[name] Title: Registered Respiratory Therapist Department: Respiratory Therapy [contact] Email: [contact]

Co-Investigator:

[name] II, M.D. Title: Surgical Trauma Physician Department: Trauma Services Email: [contact]

2) Funding Source

Financial funding was obtained by grants from local agencies through application processes, along with interviews and assessment of the medical device. The first grant was obtained through the Southern Colorado Society of Respiratory Care in hopes to obtain better choices for treatment for patients with rib fractures. Additional funding was provided by the Penrose Foundation as well.

3) Objectives and Hypothesis(es)

The purpose of this study is to use the Duracore patient operated torso splinting device for patients with chest trauma, including rib fractures, to improve deep breathing and help with reduced hospital length of stays (LOS). The hypothesis of this study is that the use of the Duracore splinting device will reduce hospital length of stays and improve patient lung capacities over the course of admission following chest trauma.

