The study will use a randomized-experimental design and will be randomized via envelope randomization, with experimenters being blinded. A total of 104 patients, 26 in each group, will undergo initial incentive spirometry and force vital capacity (FVC) and FEV₁ tests. Groups will consist of a control versus experimental group, stratified into bilateral and unilateral rib fractures. Three days' worth of data will be collected for each of the tests and will also be collected 24 hours prior to discharge. Length of stays will be compared for experimental and control groups, as well as time to ambulation (collected from the first physical therapy assessment). Injury severity score will also be collected to determine any correlation by severity of injury. Patient satisfaction surveys for the device will also be collected to determine if the patients feel a difference with the device.

4) Background/Scientific Rationale and Significance

Little research as been conducted to determine the significance of a splinting device used in patients with chest trauma, and it is still uncertain whether these devices improve overall patient outcomes. Contradicting studies with similar experimental designs show either some significance (p-value) or insignificance in pulmonary function pre- and post-treatment. This gap in current knowledge leaves room for concern in whether the patient truly benefits from a splinting device in this type of injury. Changes in percent predicted FVC/FEV₁ ratio in this patient population are not readily demonstrated in most of these studies, as well as differing length of stays. This study will contribute to this base of knowledge by determining the effects of the Duracore splinting device on this patient population using the objectives.

5) Inclusion and Exclusion Criteria

Inclusion:

- Adult patient admitted to the trauma service at Penrose Hospital
- Willing and able to comply with all requirements of the study
- Active diagnosis of rib fractures
- Male or female ages 18 and older
- Able to provide written informed consent to participate in the study
- Must be physically able to don and use the splinting device independently without assistance

Exclusion:

- <18 years old
- History of pulmonary disease, lobectomy, or lung transplant
- Current smoker of tobacco products >5 years
- Diagnosis of flail chest

- Pregnant Women
- Prisoners
- Cognitively Impaired; must be alert and oriented x 3

6) Number of Subjects

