Number of subjects was based on a power analysis using FVC/FEV₁ as the primary variable and stratified by unilateral versus bilateral diagnosis. Previous literature suggests a standard deviation of approximately 0.20-0.60 for FVC/FEV₁ values. SD was set at 0.40. Unilateral control was estimated to be 50% of predicted values (FVC/FEV₁) due to the nature of the injury, set at approximately 1.50L, with bilateral set at approximately 1.35L. Unilateral experimental group means were increased by 20% of predicted values to 1.80L, and bilateral to 1.50L. The required sample size to achieve 80% power to detect difference between splint and control groups is 104, with each group requiring 26 subjects each. Power calculations were performed in R version 4.0.0 with the pwr2ppl package, using the anova2x2 function.

Number of subjects to be used are 150 to account for withdrawals, incomplete data sets, extraneous results, etc. This is a single site study.

7) Recruitment Methods

Respiratory Therapy is part of the trauma multi-disciplinary team. and is involved with the care of every trauma patient admitted to Penrose Hospital. During trauma rounds in the ICU and floor patients that met criteria for the study will be identified. The investigators will approach those identified patients for potential enrollment in the study. Note they will not approach any patient for consent that is under their care that shift. There are no flyers or advertisements for this research or device.

8) Study Timelines

It is estimated that it will take at least one year to complete this study to include enrollment, subject completion, and all analysis. All primary variables and analyses should be completed by this time.

9) Study Endpoints

The primary endpoint of this study is to investigate the use of the Duracore splinting device in patients with chest trauma. Hospital length of stays, time to ambulation, a patient satisfaction survey, incentive spirometry, forced vital capacity measurements, and the injury severity score will be correlated to a control group to determine its' effectiveness. The quantitative data points will be collected over the first three days of hospital stay and 24 hours prior to discharge. The qualitative data will be collected prior to patient discharge. The hypothesis of this study is that the use of the Duracore splinting device will reduce hospital length of stays and improve patient lung capacities over the course of admission following chest trauma.

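### The primary endpoint is not fixed: no section chooses between FVC and FEV₁, a scale for the test, or an analysis time point

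*Combined protocol and SAP*

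**What the plan says.** - **Variable used for sizing.** Section 6: "Number of subjects was based on a power analysis using FVC/FEV₁ as the primary variable and stratified by unilateral versus bilateral diagnosis". The inputs are in litres: "Unilateral control was estimated to be 50% of predicted values (FVC/FEV₁) due to the nature of the injury, set at approximately 1.50L", with bilateral control at 1.35 L. Then: "Unilateral experimental group means were increased by 20% of predicted values to 1.80L, and bilateral to 1.50L". The SD is 0.40 with no unit. Section 11 repeats this.
- **Separate tests or a ratio.** Section 3 says patients "will undergo initial incentive spirometry and force vital capacity (FVC) and FEV₁ tests". Section 4 uses the same slash term for a ratio when describing other studies: "Changes in percent predicted FVC/FEV₁ ratio in this patient population are not readily demonstrated".
- **Scale.** The variable list in section 9 and the procedures in section 10 provide for calculating percent predicted; section 10 gives reduction of statistical error as the reason. Section 11 does not say which scale is tested.
- **Endpoint section.** Section 9: "The primary endpoint of this study is to investigate the use of the Duracore splinting device in patients with chest trauma". It then lists length of stay, time to ambulation and the survey, followed by: "incentive spirometry, forced vital capacity measurements, and the injury severity score will be correlated to a control group". FEV₁ is not in that sentence.
- **Hypothesis.** Sections 3 and 9 say the device "will reduce hospital length of stays and improve patient lung capacities over the course of admission".
- **Timing.** Spirometry is done at baseline before allocation, over three days, and again before discharge (sections 3, 9 and 10).
- **Analysis.** Section 11 plans a two-tailed t-test for both incentive spirometry and FVC/FEV₁. It does not mention strata, baseline or alpha.

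**The concern.** A confirmatory result needs one pre-named quantity. Here the primary variable could be FVC or FEV₁, in litres or percent predicted, at any of three or four collections, as a raw value or as a change from baseline. Incentive spirometry receives the same test, and length of stay comes first in the hypothesis without being ranked. Each choice is defensible once the data are in hand, so a p-value below 0.05 would not carry a 5% error rate. The sample size also cannot be tied to a result, because 104 applies only to a single measurement in litres with SD 0.40.

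Two smaller points sit beside this. The assumed unilateral gain is described as a percentage of predicted that its own litre values do not give. And the trial was sized with a 2x2 ANOVA, while the planned t-test does not mention the strata.

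**Working it through.** **1. The plan's own number.** Inputs from section 6: control 1.50 L and 1.35 L, experimental 1.80 L and 1.50 L (unilateral, bilateral), SD 0.40 read as litres, 26 per cell. Two-sided alpha 0.05 is assumed, since none is stated.
- Treatment effect = (0.30 + 0.15)/2 = 0.225 L.
- Standard error = 0.40 × √(4/104) = 0.0784; noncentrality = 0.225/0.0784 = 2.87 on 100 df.
- Power = 81.1%. With 25 per cell it is 79.5%, so 26 per cell (104) reproduces.
- At 104, the SD range of 0.20-0.60 cited in section 6 spans power from over 99.9% down to 47%, so the SD must belong to the chosen measure.

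**2. The percentage wording.**
- Predicted = 1.50/0.50 = 3.00 L.
- Unilateral gain: 0.30/3.00 = 10% of predicted; 1.80/1.50 = 20% relative to control. A gain of 20% of predicted would be 0.60 L, giving 2.10 L.
- Bilateral gain: 0.15/1.35 = 11% relative.

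**3. Late choice of the primary result.** Multivariate normal test statistics, true effect zero, a positive result if any |z| > 1.96, one scale only. The correlations are assumptions: FVC with FEV₁ 0.7-0.9, between days 0.6-0.9.

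| Freedom | False positives |
|---|---|
| FVC or FEV₁, one time | about 7-8% |
| Both volumes, three collections | 11.5-19.1% |
| Both volumes, four collections | 12.8-23.0% |

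**4. Analysis and strata at N = 104.** For unilateral share u, the size-weighted effect is 0.30u + 0.15(1 − u). The t-test that ignores strata has SD √(0.16 + u(1 − u)(0.15² + 0.30²)/2), which is 0.417 at u = 0.5. The adjusted analyses use residual SD 0.40.

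| Unilateral share | Effect (L) | Pooled t-test | Adjusted, strata weighted by size | Adjusted, strata weighted equally |
|---|---|---|---|---|
| 40% | 0.210 | 72.1% | 75.5% | 79.5% |
| 50% | 0.225 | 77.8% | 81.1% | 81.1% |
| 60% | 0.240 | 82.9% | 85.8% | 79.5% |
| 70% | 0.255 | 87.4% | 89.6% | 74.0% |

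If the model has treatment and stratum but no interaction term, the residual variance also picks up u(1 − u) × 0.15²/4. At u = 0.5 this is 0.0014, and power is 80.7% instead of 81.1%.

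Simulating the pooled t-test with exactly 26 per cell gives 78.6%. At the section 18 floor (0.70 × 150 = 105), with an equal split, the adjusted analysis has 81.4% and the pooled t-test 78.2%. If all 150 are evaluable, they have 92.8% and 90.7%.

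**5. If percent predicted were chosen.** The largest SD that keeps 80% at 104 is 0.406 L. With predicted at 3.00 L for every patient (assumed), that is 0.406/3.00 = 13.5 percentage points. The documents give no SD on this scale.

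**The case against.** The best defence is that sections 6 and 11 do name a primary variable, that the litre values and the two separate tests show the slash means FVC and FEV₁, and that section 9 leans towards FVC. The ratio reading is indeed weak: the word appears once, in background on other studies. But reading the term as both volumes still leaves two measures and no time point, and a lean is not a choice.

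Several stronger readings are tempting and are not supported:
- *The analysis is fixed as percent predicted and contradicts the power calculation.* Sections 9 and 10 plan to calculate that scale; section 11 leaves the tested scale open. It is unspecified, not contradictory.
- *The percentage slip leaves the trial short of patients.* The calculation used litres, and 104 reproduces. The 20% is stated for the unilateral group only, so the bilateral 11% is not a contradiction.
- *The 2x2 ANOVA used for sizing is simply better than the t-test.* With strata weighted equally it loses when unilateral cases predominate: 79.5% against 82.9% at a 60% share, and 74.0% against 87.4% at 70%. Weighting strata by size beats the pooled t-test at every split tried.
- *The trial's error rate is 12-23%.* The documents give no correlations, so this is an illustration. It leaves out scale, baseline handling, incentive spirometry and length of stay.

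It is also fair to say that pooling is only one reading of section 11. Separate t-tests within strata, at 26 per cell, would have about 76% power (unilateral) and 26% (bilateral). And since the hypothesis concerns the course of admission, a summary over the collections is as legitimate as a single day.

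**Conclusion.** The point stands and must be fixed before outcomes are examined: as written, no single test controls the error rate. This rests on the text alone. The 7-23% figures only illustrate the size and depend on the assumed correlations.

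The sample size is sound for one measurement in litres with SD 0.40 and alpha 0.05. The analysis mismatch is small under the pooled reading, about 3 points at an equal split. With 104 evaluable and strata weighted by size, the stated 80% holds only if about half or more of the patients are unilateral; the documents give no expected split beyond 26 per group. The percentage wording is a minor correction.

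**What to change.** In sections 6, 9 and 11:
1. Name one primary measure (FVC or FEV₁), one scale, and either one already-collected time point or one summary over the collections. These are the sponsor's choices. In litres the sentence could read: 'The primary endpoint is FVC in litres at [named collection or summary].'
2. State how the baseline value enters, for example as a covariate.
3. Label everything else secondary: the other volume, the ratio, the other scale, other days, incentive spirometry, length of stay, time to ambulation and the survey.
4. Make the primary analysis the treatment effect adjusted for the unilateral/bilateral stratum (treatment plus stratum, so that strata are weighted by size), and state alpha.
5. Restate the assumed effect as +0.30 L unilateral (10% of predicted, 20% relative to control) and +0.15 L bilateral (11% relative). Confirm that SD 0.40 is in litres for the chosen measure.

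The cost is wording and one analysis line. No tests are added, and no patients if the SD is confirmed and about half or more are unilateral. Only one measure can be claimed as primary, so length of stay and incentive spirometry become supportive; making length of stay primary would need its own sample size, because none is given. Litres match the existing calculation but give up the adjustment for height, sex, ethnicity and age that section 10 wants. Percent predicted keeps it but needs means, SD and N restated.

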The design of this study is a randomized experimental trial. The procedures involved in this study will first include obtaining the individual's consent to participate. Incentive spirometry is a standard of care that has been proven to improve deep breathing for patients. FVC/FEV₁ measurements are not always routinely done at this site but has been proven to be an indicator in respiratory deterioration in this population. Enrollment of each subject will be on a one to one basis for control and experimental groups. The trial will be randomized to reduce bias by randomly selecting patients between control and experimental groups by alternating every other patient receiving the treatment. Height, sex, ethnicity, and age will be accounted for as well to calculate the percent predicted FVC/FEV_1 to reduce statistical error. Enrollment will be based on patient consent. After enrollment into the study after admission to the hospital, baseline values of incentive spirometry (IS) and spirometry will be done. The patient will then be placed in the experimental or control group after being assigned a group via envelope randomization. If the patient is under experimental, they will receive a splinting device for treatment. Control groups will receive standard of care treatment without the splinting device. Continued analysis of IS and FVC/FEV₁ will occur over three days, and a final collection prior to discharge. Discharge planning will be coordinated with respiratory therapy, so the patient does not go home without completing the survey and final analysis. The patient satisfaction survey will be a paper survey administered to the patient. Patient identifying information will not be present on this form to maintain confidentiality. The patient will be asked if they would like to complete the form and that it is an anonymous short survey to help with identifying how the patient felt about the research. The subject will only be enrolled in the study for the duration of their hospital stay as an inpatient. There will be no follow-up after discharge, and any patients who are discharged without completing the final analysis will be omitted from the study.

11) Data Analysis Plan

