Data analysis will include a two-tailed t-test to account for significance between control and experimental groups. This will be done with both incentive spirometry and FVC/FEV₁. Correlations will be made with time to ambulation and length of stays, as well as injury severity score. Graphic representation of trends will also be used to demonstrate differences between the groups. Qualitative analysis will include providing averages from the questionnaire using a Likert scale. These averages will be used to determine whether the population felt the device provided any help with their chest trauma. Number of subjects was based on a power analysis

using FVC/FEV₁ as the primary variable. Previous literature suggests a standard deviation of approximately 0.20-0.60 for FVC/FEV₁ values. SD was set at 0.40. Unilateral control was estimated to be 50% of predicted values (FVC/FEV₁) due to the nature of the injury, set at approximately 1.50L, with bilateral set at approximately 1.35L. Unilateral experimental group means were increased by 20% of predicted values to 1.80L, and bilateral to 1.50L. The required sample size to achieve 80% power to detect difference between splint and control groups is 104, with each group requiring 26 subjects each. Power calculations were performed in R version 4.0.0 with the pwr2ppl package, using the anova2x2 function. Number of subjects to be used are 150 to account for withdrawals, incomplete data sets, extraneous results, etc. This is a single site study.

Patient satisfaction surveys will use a numbered Likert Scale. The averages of each answer will be used to reinforce the efficacy of the device and correlate to primary data. Randomization will occur by experimenter-blinded envelope randomization.

12) Provisions to Monitor the Data to Ensure the Safety of Subjects

Subjects will be monitored for the duration of their stay by all staff members, and any adverse events related to the device itself will be reported accordingly. This device claims minimal risk to patients due to its unrestrictive and non-invasive nature but will be monitored by investigators for any adverse effects. **The Data Safety Monitoring staff will review all documentation accordingly at least quarterly.**

13) Withdrawal of Subjects

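### A t-test on a fixed hospital day, or on complete three-day sets, would leave out patients already discharged, and the plan neither names its time point nor says how early discharge is handled.

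*Combined protocol and SAP*

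**What the plan says.** - **Schedule.** Section 3: "Three days' worth of data will be collected for each of the tests and will also be collected 24 hours prior to discharge". Section 10 adds a baseline test before assignment and a final collection before discharge.
- **Observation ends at discharge.** Section 10: "The subject will only be enrolled in the study for the duration of their hospital stay as an inpatient". There is no follow-up afterwards.
- **Hypothesis.** Sections 3 and 9 expect the splint both to shorten stay and to improve lung capacity.
- **Analysis.** Section 11: "Data analysis will include a two-tailed t-test to account for significance between control and experimental groups". It applies to incentive spirometry (IS) and FVC/FEV₁. No hospital day or other time point is named.
- **Size.** Sections 6 and 11: "The required sample size to achieve 80% power to detect difference between splint and control groups is 104, with each group requiring 26 subjects each".
- **Missing data.** The same sections add: "Number of subjects to be used are 150 to account for withdrawals, incomplete data sets, extraneous results, etc". Section 18 says that 70% of the 150 is enough. The documents contain no definition of an incomplete set, no intention-to-treat statement and no rule for patients discharged before the third daily test.

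**The concern.** A patient who goes home before the third daily test cannot supply that reading. Whether the reading exists therefore depends on length of stay, which the splint is expected to change. A t-test takes one value per patient, so with several daily readings it is natural to pick a day or to keep only full sets. Either choice compares the patients still in hospital, and these may be different kinds of patient in the two arms. If the splint works and the best-recovering patients leave first, the splint arm loses more of its good values than the control arm does. Enrolling more patients under the same selection restores the number analysed but leaves the bias in place.

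**Working it through.** **1. The plan's own figure.** The inputs are in sections 6 and 11: "SD was set at 0.40"; control means "set at approximately 1.50L, with bilateral set at approximately 1.35L"; and "Unilateral experimental group means were increased by 20% of predicted values to 1.80L, and bilateral to 1.50L". Alpha is not stated, so two-sided 0.05 is assumed.

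- Average difference: (1.80 − 1.50 + 1.50 − 1.35)/2 = (0.30 + 0.15)/2 = 0.225 L.
- Main effect in a 2×2 ANOVA with N = 104: 0.225 / (0.40 × √(4/104)) = 2.87. Noncentral F on 1 and 100 df gives 81.1% power. With 25 per cell (N = 100) power is 79.5%, so 26 per cell is the smallest size that reaches 80%. The 104 reproduces.
- Allowance: 104/0.70 = 149, close to the stated 150. 150 − 104 = 46, or 30.7% of enrolment.
- With 75 per arm and no losses, noncentral-t power for 0.225 L and SD 0.40 is about 93%.

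**2. Illustration: discharge driven by day-2 volume.** The documents give no early-discharge rate and no link between volume and discharge, so everything in this step is assumed. There are 1,000,000 simulated patients per arm. The between-patient SD is 0.35 and the within-patient SD 0.20 (total √(0.35² + 0.20²) = 0.40). The control mean rises 0.10 L a day from 1.125 L to 1.425 L on day 3, which is the average of 1.50 and 1.35. The splint effect grows evenly to 0.225 L on day 3. Patients whose day-2 volume passes a threshold (1.84, 1.70 or 1.60 L) leave before the day-3 test. The t-test uses those who remain.

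| Leave early, control / splint | Observed day-3 difference | Effect lost | Power, 104 assigned | Power, 75 per arm assigned | Power, replaced to 52 per arm |
|---|---|---|---|---|---|
| 10% / 18% | 0.186 L | 17% | 67% | 82–83% | 74% |
| 18% / 29% | 0.174 L | 23% | 59% | 75% | 71% |
| 25% / 38% | 0.167 L | 26% | 53% | 69% | 70% |

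Example, first row at 75 per arm: about 67.4 and 61.3 patients remain. Selection narrows the SD to about 0.36. The ratio is 0.186 / (0.362 × √(1/67.4 + 1/61.3)) = 2.91, which gives about 82%. The last column shows that replacing the lost patients does not bring back the planned 81%.

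**3. Weaker link.** Independent noise is added to the discharge score, with the same control loss rates. With noise SD 0.40 L the effect lost is about 8% to 13%. With noise SD 0.80 L it is about 3% to 5%.

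**4. Loss rates set directly.** Here rho is the within-arm correlation between lung volume and early discharge, and the true effect is 0.225 L.

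| Loss, control / splint | rho 0 | rho 0.3 | rho 0.5 | rho −0.3 |
|---|---|---|---|---|
| 10% / 20% | 0.225 | 0.207 | 0.194 | 0.244 |
| 20% / 35% | 0.224 | 0.199 | 0.182 | 0.253 |
| 20% / 20% | 0.226 | 0.226 | 0.225 | 0.225 |

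Bias is absent, apart from simulation error, at rho 0 or with equal loss. With unequal loss it is about −8% to −19% at rho 0.3 to 0.5, and +8% to +12% at rho −0.3.

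**5. Does the remedy work?** In the scenarios of steps 2 and 3, day-3 values were predicted from the earlier readings within each arm, and the contrast was taken over all assigned patients. This stands in for the mixed model. It returned about 0.225 L each time. That is expected, because simulated discharge depended only on an observed reading and independent noise.

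**The case against.** The strongest reply is that the plan does not prescribe the analysis that would be biased.

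- A reader might infer that patients lacking one of the three days count as incomplete and are dropped or replaced. No section says so. The only stated omission, in section 10, is for patients discharged without the final test, and section 13 says data are retained unless the subject specifies otherwise.
- A reader might infer that day 3 is the planned comparison. Section 11 names no day, and the t-test could equally use the pre-discharge value. Early leavers should have a baseline and a final reading, because section 10 coordinates discharge with respiratory therapy for that purpose.
- A reader might infer that the splint effect will be understated. That needs both more early discharge on splint and better volumes among early leavers. The first follows from the trial's hypothesis. The second is plausible but is not documented. Withdrawal for deterioration, allowed by section 13, is a further loss whose effect depends on the arm that it falls in.
- A strict day-2 threshold is close to the strongest possible selection on that reading, and power at 104 assigned ignores the planned 150. At 75 per arm the mildest scenario still exceeds 80%.

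All of this stands, and it limits the point to a conditional one. It does not remove the gap: the plan leaves the time point and the handling of early discharge open, and its only safeguard is a larger number of patients.

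**Conclusion.** The point holds in conditional form. If IS and FVC/FEV₁ are compared by t-test on a fixed day, or only in patients with all three days, the comparison selects on length of stay, and the extra enrolment cannot correct that. If the splint works as hypothesised and better volumes go with earlier discharge, the likely direction is toward no effect.

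Under assumed discharge patterns, about 3% to 26% of a true 0.225 L is lost. At the planned 75 per arm, with discharge set strictly by day-2 volume, power is about 82–83%, 75% and 69% when 10%, 18% and 25% of controls leave early, against about 93% with no losses. These figures illustrate the size of the problem and do not predict it. The documents supply no early-discharge rate, and they do not support the stronger claims that early leavers will be excluded or that the result will be biased downward.

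**What to change.** In section 11:

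1. State that discharge before the third daily test does not make an assigned patient an incomplete data set, and that no patient is dropped or replaced for that reason.
2. Replace the t-test on IS and FVC/FEV₁ with a repeated-measures mixed model with terms for arm, day and arm by day, the baseline reading, and the unilateral/bilateral stratum. Fit it to all available daily readings from every assigned patient.
3. Name in advance the time point at which the arm contrast is taken.
4. Report by arm the number already discharged at each test.

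The cost is analysis wording only, with no new data and no extra patients. The downside is that the model assumes early discharge is explained by the readings already observed. Discharge for reasons related to unrecorded recovery would leave some bias, and the counts in item 4 let a reader judge how much could be at stake.

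### Length of stay ends at a discharge judgement that the plan neither blinds nor separates from the investigators; the role-separation rule covers only the consent approach

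*Combined protocol and SAP*

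**What the plan says.** **Length of stay is in the hypothesis.** Section 3 states that "the use of the Duracore splinting device will reduce hospital length of stays and improve patient lung capacities over the course of admission", and section 9 repeats it. The design paragraph of section 3 adds: "Length of stays will be compared for experimental and control groups, as well as time to ambulation".

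**Who the investigators are.** Section 1 lists four. Three are respiratory therapists. The fourth is listed with "Title: Surgical Trauma Physician Department: Trauma Services".

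**Where the participants are.** Section 5 requires an "Adult patient admitted to the trauma service at Penrose Hospital". Section 7 says that respiratory therapy "is involved with the care of every trauma patient admitted to Penrose Hospital".

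**How discharge is linked to the study.** Section 10: "Discharge planning will be coordinated with respiratory therapy, so the patient does not go home without completing the survey and final analysis".

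**What separates the roles.** Section 7, on recruitment: "Note they will not approach any patient for consent that is under their care that shift". Section 18 also says that the respiratory therapy department carries out only ordered procedures and is not directly part of the research. It then counts the investigators among the staff who perform those procedures, and it does not mention discharge.

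**Blinding.** Section 3 says that experimenters are blinded, and section 11 attaches this to the envelope step. Neither mentions the treating or discharging clinicians. Under section 10 the control arm has no device, under section 18 the investigators teach hospital staff what the device is, and under section 26 device users are checked daily for adverse effects.

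**The concern.** Length of stay is recorded objectively, but a judgement produces it. If a person who holds the hypothesis and can see the arm takes or shapes that judgement, a small preference in timing enters the outcome directly. It would look the same as a device effect.

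The protocol already accepts that investigators who also treat patients need a boundary, but it draws that boundary only around the consent approach. Nothing comparable covers the later decision that fixes one of the two hypothesised effects.

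The variable list in section 9 has no item for who made or advised on the discharge decision. If the question were raised after the trial, the data could not answer it.

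This differs from discharge being held back for the final test, and from the question of who performs the lung function tests.

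**Working it through.** **1. The plan's own figure, which gives the arm size.** Sections 6 and 11 size the trial on FVC/FEV₁, not on length of stay. Inputs: SD 0.40; control means 1.50 and 1.35; splint means 1.80 and 1.50. The alpha level is not stated, so 0.05 two-sided is assumed.
- Average splint effect = (0.30 + 0.15)/2 = 0.225.
- Noncentrality for the main effect in the 2×2 ANOVA = 4n × (0.1125/0.40)². For n = 26 per cell this is 8.23, with 1 and 100 df.
- Power is 81.1% at 26 per cell and 79.5% at 25 per cell.

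So 26 per cell, 104 in all, reproduces. With 1:1 allocation that is 52 per arm. Nothing in this point changes that figure.

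**2. The passages side by side.**

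| Question | What the documents give |
|---|---|
| Does length of stay matter to the claim? | Yes: hypothesis (sections 3 and 9) and a comparison between arms (section 3) |
| Who decides discharge? | Not stated |
| Do investigators have a route to it? | One is a trauma service physician (section 1); the department of the other three coordinates discharge planning (section 10) |
| Can the arm be seen at the bedside? | By inference yes: torso device, no sham, staff taught to know it |
| Is the discharging clinician blinded? | No passage says so |
| Is there a rule keeping investigators out? | For consent on that shift only (section 7); section 18 concerns procedures |

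**3. Illustration of size.** The documents give no SD for length of stay. Assume SD 3, 4 or 6 days, 52 per arm, no true effect, and a two-sided 5% t-test. Let d be the shift in days for an affected discharge and p the share of splint-arm discharges affected.
- Arm-level shift = p × d.
- Noncentrality = (p × d / SD) × √(52/2), with 102 df and critical value 1.983.
- Example: p = 0.25, d = 0.5 gives a shift of 0.125 day. At SD 3 the noncentrality is 0.0417 × 5.099 = 0.21.

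Probability of a significant result, against 5% with no shift:

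| Share affected, shift each | Arm-level shift | SD 3 | SD 4 | SD 6 |
|---|---|---|---|---|
| 25%, half a day | 0.125 day | 5.5% | 5.3% | 5.1% |
| 50%, half a day | 0.25 day | 7.1% | 6.1% | 5.5% |
| 100%, half a day | 0.5 day | 13.4% | 9.7% | 7.1% |
| 100%, one day | 1 day | 39.1% | 24.3% | 13.4% |

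These are two-sided rates. Counting only results that falsely favour the splint, the baseline is 2.5%, and the half-day whole-arm row becomes 13.2%, 9.2% and 6.2%.

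The share affected drives the result. The documents do not give it, so no single row can be called the expected one.

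**The case against.** **The key premise is inferred.** No passage says who decides discharge, or that the physician co-investigator discharges enrolled patients; section 1 gives only a title and a department. This stands. A reader might infer that investigators do control discharge, or that splint patients will be sent home sooner. The documents support neither. They show access without a rule.

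**The plan says experimenters are blinded.** It does, without defining the term. Where section 11 explains it, it belongs to the envelope step. It is hard to extend to a clinician examining a patient in a torso splint. That the trauma service is unblinded remains an inference, though a strong one.

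**Section 18 already limits the department.** It limits what the department does in procedures, includes investigators among those doing them, and does not cover the physician or discharge. It should be read with section 7, but it does not close the gap.

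**The exposure is narrow.** Three of the four investigators are therapists, and nothing says they take discharge decisions. This largely stands. Their route is the coordination in section 10, whose stated purpose is to complete the survey and final test. It is also why whole-arm shifts are an upper illustration.

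**The modelled test may not be the planned one.** Section 11 assigns the t-test to incentive spirometry and FVC/FEV₁ and speaks of correlations for length of stay; section 3 says only that length of stay is compared. This stands too, so the rates illustrate scale and do not describe the plan's own test.

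**Any trial of a visible device has this problem.** True of the general open-label bias. The part that runs through an investigator can be avoided at little cost.

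**Conclusion.** The concern holds as an avoidable opportunity for bias. Length of stay is part of the hypothesis, it ends at a judgement, investigators have a possible route to that judgement, and no passage blinds it or keeps them out. Size and direction are unknown.

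If investigators could influence only a minority of discharges, the effect on the error rate is slight: about 5.1% to 5.5% against 5% when 25% of discharges move by half a day. It becomes material only if the shift is spread across the arm: 7% to 13% for half a day. All of these rest on an assumed SD of 3 to 6 days, an assumed shift, alpha 0.05 and a t-test. The larger rates for a one-day whole-arm shift should not be read as what this trial will produce.

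The sample size and the lung function comparison are unaffected. The change is worth making because it is cheap and because, as planned, the trial would hold no record with which to answer the question later.

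**What to change.** 1. **Section 7.** Extend the rule: when another trauma clinician is available, no study investigator takes or advises on the discharge decision for an enrolled patient. Limit the respiratory therapist investigators' part in discharge coordination (section 10) to scheduling the final test and survey. State who makes the discharge decision and who is and is not blinded. Discharge criteria are unchanged.
2. **CRF.** Add one field: whether a study investigator was involved in the discharge decision.
3. **Analysis (section 11).** Report that field by arm, descriptively. Keep all randomised patients in the length-of-stay comparison. Do not drop those with investigator involvement, even as a sensitivity check: involvement arises after randomisation and may depend on arm, so excluding on it can create bias. For the same reason, the section 10 omission of patients who miss the final test should not carry over to length of stay, which is known without that test.
4. **Report.** State as a limitation that other clinicians can see the splint.

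**Cost.** A few sentences, one CRF field and one descriptive table, plus a small rota constraint for one physician. Residual open-label bias from the other clinicians remains; the change reduces the problem and does not remove it.
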